4.2 Inclusion criteria

Patients must meet all of the following inclusion criteria to be eligible for enrolment into the study:

1. Written informed consent obtained from the patient prior to performing any protocol-related procedures, including screening evaluations.
2. Female or male, Age \geq 18 years at time of study entry.
3. Primitive triple negative breast cancer proven histologically, defined according to the following criteria:
 - ⇒ Estrogen receptors \leq 10%.
 - ⇒ And progesterone receptors \leq 10%.
 - ⇒ And HER2 not amplified or not overexpressed.
4. Metastatic Breast Cancer documented by conventional imaging and/or FDG PET/CT with at least one measurable metastatic lesion according to RECIST and/or PERCIST.
5. Consent to use a contraception method for at least 30 days after administration of ^{89}Zr -TLX250.
6. ECOG Performance Status 0 or 1.
7. Life expectancy at least 6 months.
8. Patient has valid health insurance.
9. Patient is willing and able to comply with the protocol for the duration of the study including undergoing treatment and scheduled visits and examinations including follow up.

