5.2.3 Imaging Analysis

5.2.3.1 ⁸⁹Zr-TLX250 Tumor Targeting

⁸⁹Zr-TLX250 tumor uptake will qualitatively be assessed, considering whether or not ⁸⁹Zr-TLX250 binding the target lesions determined on FDG PET-CT as metastatic lesions.

The interpretation of the ⁸⁹Zr-TLX250 PET/CT images as positive or negative for metastatic TNBC will be made on the basis of visual examination only.

The ⁸⁹Zr-TLX250 PET/CT images will be evaluated for evidence of radioactive uptake in the metastatic TNBC lesions. The local and central reviewers will designate the lesions as having a status of positive or negative.

The ⁸⁹Zr-girentuximab PET/CTs will be assessed in a central reviewing system to ensure true lesion detection and reproducible inter-observer agreement. All ⁸⁹Zr-girentuximab PET/CTs would be assessed by two expert nuclear physicians independently.

The first evaluation will be done by the nuclear physician, in charge of the patient during the ⁸⁹Zr-girentuximab PET/CT exam.

The second evaluation will be done by a second nuclear physician who should be blinded for evaluation of the first nuclear physician. However, for patient safety reasons, the nuclear physician should be allowed to communicate findings that required (local) interventions (e.g. brain metastases).

The two reports would be harmonized to one final report by the first reviewer. In case of different findings, a third nuclear physician should evaluate the ⁸⁹Zr-girentuximab PET/CT exam to reach a consensus.

A tumor lesion will be defined visually positive based on anatomical substrate on low-dose CT in combination with ¹⁸FDG and/or ⁸⁹Zr-girentuximab-uptake. Quantification of positive lesions as defined by evaluation reports for ¹⁸FDG and ⁸⁹Zr-girentuximab PET/CT will be performed by drawing regions-of-interest using dosisoft (PLANET Edition 3 – PLANET Onco Dose, Version 3.1.1.50 – 2021-01-03).

The maximum and mean standardized uptake values (SUV) will be calculated. SUVmax will be used for tumor tracer-uptake; SUVmean for measuring uptake in healthy organs and blood pool.

The lesion will be classified as PET-positive if:

- Radioactivity in the lesion is clearly visible (as described above), **AND**
- With a same location as FDG positive lesions described previously.

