8. STATISTICAL METHODS AND SAMPLE SIZE DETERMINATION

The analysis will cover 12 patients.

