8.1 Brief reminder of study objectives

8.1.1 Primary objective

To assess the concordance for tumor lesion detection using ^{89}Zr -TLX250 PET/CT versus a conventional ^{18}FDG PET/CT scan where comparison will be made on a per lesion analysis basis.

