8.2 Determination of sample size

As this study is a proof-of-concept, exploratory and descriptive pilot study, the sample size determination is not based on statistical considerations, it is planned to enrol 12 evaluable patients.

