8.8 Description of analysis sets

8.8.1 For Safety Analysis Set:

The frequency and severity of the clinical and biological effects collected over a period of 15 days then at 3 months following the completion of the ^{89}Zr -TLX250 PET/CT will be described by means of frequency of their respective modalities. HACA test at the visit at 3 months post ^{89}Zr -TLX250 PET/CT.

8.8.2 For the determination of ^{89}Zr -TLX250 PET-CT preliminary analysis of diagnostic performance:

From the reference ("gold standard") determined for each patient from all imaging and histology screening data and/or 3-months imaging follow-up (RECIST 1.1 criteria, or PERSIST criteria). The reporting qualitative and semi-quantitative parameters of the lesions will be established at D5 post-injection. The diagnostic performance of ^{89}Zr -TLX250 PET/CT obtained at the post-injection delay considered optimal related, ^{18}FDG PET/CT scan and CT scan compared to gold standard will be described by the sensitivity, specificity, positive and negative predictive values (with their 95% CI) and compared by means of Mc Nemar test. Concordance between techniques will be described by means of Kappa.

Total number of lesions (gold-standard) will be the number of lesions identified by at least one modality.

Lesion detection rates per imaging modality and combined imaging modalities (CT combined with PET) will be estimated with their 95% CI and compared by Wald test, overall and according to organ sites.

Agreement in detecting lesions between modalities will be assessed using kappa's (95%CI).

Furthermore, we will compare the median number of affected organ sites across patients assessed by ^{18}FDG -PET/CT or ^{89}Zr -girentuximab-PET/CT using Wilcoxon signed rank tests.

The physiological biodistribution of ^{89}Zr -girentuximab will be described in normal tissues (lung, liver) using geometric mean SUVmean.

Short Title : **OPALESCENCE**
Ref ICO : ICO-2020-25
N° EudraCT : 2020-003805-71

The overall geometric mean ⁸⁹Zr-girentuximab or ¹⁸FDG SUVmax will be used to quantify uptake in lesions. Link between uptake and lesions location and lesions diameter on CT will be tested.

Correlation between ¹⁸FDG -uptake and ⁸⁹Zr-girentuximab-uptake will be calculated by Rho's coefficient (Spearman test).

8.8.3 For ancillary study set:

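### Section 8.8.2 does not make the patient the cluster for per-lesion detection rates and sensitivity, so ordinary 95% CIs will be too narrow if positivity is correlated within patient

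*Combined protocol and SAP*

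**What the plan says.** The unit of analysis is the lesion: section 8.1.1 states that "comparison will be made on a per lesion analysis basis". The number of patients is fixed: "The analysis will cover 12 patients" (section 8). Inclusion criterion 4 in section 4.2 requires "at least one measurable metastatic lesion" and sets no upper limit, so one patient may supply many lesions.

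Section 8.8.2 plans 95% CIs for sensitivity and for detection rates by modality. The detection rates "will be estimated with their 95% CI and compared by Wald test, overall and according to organ sites". The denominator appears to be pooled over patients: "Total number of lesions (gold-standard) will be the number of lesions identified by at least one modality". The same section also describes a reference standard "determined for each patient from all imaging and histology screening data", so per-lesion sensitivity is a reading of the text and is not stated outright.

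The formula for the CIs is not named. No section mentions the patient as a cluster, within-patient correlation, a robust variance, GEE, a mixed model or a cluster bootstrap. Section 8.7 speaks only of keeping missing data low. The one comparison in 8.8.2 made across patients is the signed-rank test on the number of organ sites involved, and it does not bear on these CIs.

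**The concern.** Lesions from one patient share tumour biology, the injected dose, the scan session and the readers. If they tend to be positive or negative together, 60 lesions from 12 patients carry less information than 60 independent lesions. A binomial CI computed on the lesion total ignores this and is too short.

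Section 8.2 calls this an "exploratory and descriptive pilot study". There is no success rule, so no decision turns on these CIs. But in a descriptive study the estimates and their intervals are the main product, and section 13 says that the results will be submitted for publication. Detection rates and sensitivity could be reported with error bars that overstate what 12 patients can show. If the method is left open until the lesion data are seen, the choice between narrow and wide intervals is made after the fact.

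**Working it through.** **Inputs from the documents.** 12 patients (sections 8 and 8.2), lesion as unit (2.1.1 and 8.1.1), 95% confidence (8.8.2), at least one lesion per patient (4.2). The sample size is stated not to rest on statistical considerations, so there is no planned precision to reproduce.

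**Assumptions (not in the documents).** Mean lesions per patient m = 3, 5 or 10; true rate p = 0.25 to 0.70; ICC 0 to 0.5. The 25% CAIX expression rate in sections 1.2 and 1.3 is a share of tumours and serves only as an anchor for p. It says nothing about the ICC. Section 1.2 also ties CAIX to tumour size, so lesions of one patient may differ.

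**Step 1: design effect, equal lesion counts.** DEFF = 1 + (m − 1) × ICC. Effective n = 12m / DEFF. Half-width = 1.96 × √(p(1 − p)/(12m)) × √DEFF. Approximate coverage of the ordinary CI = 2Φ(1.96/√DEFF) − 1.

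For p = 0.25 and m = 5: 1.96 × √(0.1875/60) = 11.0 points. At ICC 0.3, DEFF = 1 + 4 × 0.3 = 2.2, effective n = 60/2.2 = 27, and half-width = 11.0 × √2.2 = 16.3 points.

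| m (lesions) | ICC | DEFF | Effective n | Half-width, ordinary → clustered | Approx. coverage of ordinary CI |
|---|---|---|---|---|---|
| 5 (60) | 0.1 | 1.4 | 43 | 11.0 → 13.0 | 90% |
| 5 (60) | 0.3 | 2.2 | 27 | 11.0 → 16.3 | 81% |
| 5 (60) | 0.5 | 3.0 | 20 | 11.0 → 19.0 | 74% |
| 10 (120) | 0.1 | 1.9 | 63 | 7.7 → 10.7 | 85% |
| 10 (120) | 0.3 | 3.7 | 32 | 7.7 → 14.9 | 69% |
| 10 (120) | 0.5 | 5.5 | 22 | 7.7 → 18.2 | 60% |

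**Step 2: simulation with unequal counts.** Beta-binomial, 12 patients, 20,000 runs per setting, mean 5 to 10 lesions, p = 0.25, 0.5 and 0.7. The clustered CI uses the ratio estimator p̂ = lesions detected / lesions, variance K/(K − 1) × Σ(xᵢ − p̂nᵢ)²/N², the delta method to the logit, and t on K − 1 = 11 df. Coverage of nominal 95% CIs:

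| ICC | Wald, 1 + Poisson counts | Clopper-Pearson, 1 + Poisson | Wald, geometric (skewed) counts |
|---|---|---|---|
| near 0 | 94-95% | 96-97% | 94-95% |
| 0.05 | 88-91% | 90-94% | 84-89% |
| 0.1 | 82-89% | 86-92% | 76-85% |
| 0.3 | 66-77% | 69-82% | 56-71% |
| 0.5 | 56-69% | 59-74% | 45-61% |

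The clustered logit CI covers 95-96% (1 + Poisson) and 91-94% (geometric) across all these ICCs. Wald coverage is near nominal at ICC near 0, so the shortfall comes from clustering and not from the small sample. An exact binomial CI does not remove it.

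**Step 3: median widths at p = 0.25, 1 + Poisson counts, ordinary Wald against clustered.** ICC 0.1: 22 against 28 points with about 60 lesions, and 15 against 23 with about 120. ICC 0.3: 22 against 36, and 15 against 33.

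**Step 4: fewer lesions and organ sites (1 + Poisson, mean 3 lesions per contributing patient), at ICC 0.1 / 0.3 / 0.5.**
- 12 patients: Wald covers 90% / 83% / 77-78%; Clopper-Pearson 94-95% / 88-90% / 83-84%.
- 6 patients: Wald 87-88% / 79-82% / 73-75%; Clopper-Pearson 95-96% / 89-91% / 84-86%. The clustered CI covers 97-99% and is 53-56 / 61-65 / 68-71 points wide.
- 4 patients: the clustered CI is 74 / 81-82 / 87-88 points wide and says almost nothing.

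**The case against.** The strongest reply is that this is under-specification and not a stated wrong method. Section 8.8.2 attaches "Wald" to the test, not to the interval, and a Wald test can come from a clustered model. Harm needs an independence-based CI, positive within-patient correlation and several lesions per patient, and the documents establish none of the three. That is correct. The omission is certain and the size is not.

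Second, the study is a 12-patient pilot without a decision rule, and the primary ratio of counts in section 8.1.2 has no stated CI. This limits the consequence to reported precision, but the intervals are still planned and will be read.

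Third, with few lesions, a low ICC and an exact CI there is essentially no loss (94-95% at mean 3 and ICC 0.1). This stands and marks where the point is negligible. At ICC 0.3 and above a shortfall remains even there.

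Fourth, the remedy has limits. With skewed counts and ICC near 0 it covers about 93-94%, slightly below ordinary Wald. At ICC 0.5 with skewed counts it can be about 2.9 times as wide. The scale matters too: the same clustered variance with t(11) on the raw scale covers only about 85-93% with skewed counts. All of this stands. It is a reason to name the exact method and call it approximate, not a reason to leave it open.

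**Conclusion.** The concern holds. The protocol does not make the patient the cluster. With positive within-patient correlation and more than one lesion per patient, ordinary CIs for detection rates, and for sensitivity if it is per lesion, are too narrow. The effect ranges from negligible to severe, depending on lesion counts and an ICC that the documents do not give. It should be fixed, but it endangers no decision.

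The conclusion has these limits:
- Specificity and the predictive values are left out. If the reference is every lesion seen by some modality, no lesion is reference-negative, which is a separate problem. Under that same reference, per-lesion sensitivity equals the detection rate.
- Kappa, McNemar and Spearman may also be affected, but no size is claimed. For paired comparisons the direction depends on how within-lesion differences correlate. Section 5.2.3.1 also counts a lesion as PET-positive only "With a same location as FDG positive lesions described previously", which constrains FDG against ⁸⁹Zr.
- Greater weight for patients with many lesions follows from the per-lesion estimand and is not an error.

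**What to change.** Add a paragraph to section 8.8.2:
- **Method.** For per-lesion detection rates, and for sensitivity if it is per lesion, the patient is the cluster. Use the ratio estimator, a cluster-robust standard error on the logit scale, and t on (contributing patients − 1) df, which is 11 overall.
- **Listing.** Give lesion counts and detection proportions for each patient.
- **Counts only** where all lesions share one status (the clustered standard error is then undefined) or where few patients contribute to an organ site. Fewer than 6 is a suggestion based on the widths above.
- **Tests.** Report lesion-level p-values only from cluster-aware paired methods, or label them descriptive. A patient-level bootstrap is possible for kappa and Spearman, but with 12 patients it is approximate and its coverage was not tested here. Reconcile sections 5.2.3.1 and 8.8.2 on what counts as ⁸⁹Zr-positive before any test of FDG against ⁸⁹Zr.

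**Cost.** Text and code in software already listed in section 11.2.1 (R, Stata, SAS), with no change to patients, visits or imaging. With Poisson-type counts (mean 5 to 10), median widths against ordinary Wald are 7-9% larger at ICC near 0, 1.3-1.5 times at 0.1, 1.6-2.1 times at 0.3 and 1.9-2.6 times at 0.5. Some intervals will not be estimable: for a true rate of 95% with a mean of 5 lesions, the clustered CI is undefined in 26-30% of runs at ICC 0.5.

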1.2 Procedure background/non-clinical and clinical experience

CAIX is normally expressed in intestinal and stomach mucosa, gallbladder and testis (10), but is upregulated in several forms of cancer, including breast cancer. Indeed, CAIX is a marker for hypoxic

regions of breast tumors (9,11) and is associated with poor prognosis (12–14) and high-grade, ER-negative breast tumors (15). Its role in tumor growth and disease progression has been attributed to its ability to reduce pericellular pH in response to hypoxia (15–17), creating a toxic environment for normal cells (18). Acidic environments also facilitate the breakdown of the tumoral extracellular matrix (19) which can enhance metastatic activity (20,21).

Several studies have identified altered HIF1 α and CAIX protein expression levels to be related to poor prognosis in breast cancer (14,22–26). CAIX is expressed in 7 % of an unselected breast cancer cohort and in 25 % of TNBCs (27). CAIX expression rates increased with tumor grade ($p < 0.001$) and associations with tumor size were significant for CAIX ($p < 0.001$; positive association). Although based on only a few studies, CAIX showed profound lower expression rates in normal breast tissue and benign breast disease ($p < 0.001$), and high rates in carcinoma in situ (28). The expression levels of HIF1 α and CAIX vary depending on the intrinsic subtype, and they are increased in TNBC compared to other subtypes (22).

Three studies have investigated HIF1 α and glucose metabolism for alternative therapeutic options to overcome breast cancer resistance to adjuvant therapeutic modalities (24,29,30). More recently, in early TNBC, combined HIF1 α and CAIX protein expression may serve as an unfavorable prognostic indicator, particularly in patients receiving a cyclophosphamide-based chemotherapy or radiotherapy as well as those with basal phenotype of breast cancer (31).

CAIX has recently emerged as a very attractive therapeutic target due to the following features:

1. CAIX shows a tissue-restricted pattern and low expression levels in normal tissues, while it is induced in a broad range of cancers (32);
2. It is located on the surface of cells (33);
3. Its overexpression in cancers confers a survival advantage in hypoxia and facilitates cell migration and metastasis (34).

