5.2.3.2 Semiquantitative ⁸⁹Zr-TLX250 Tumor Targeting

SUVs will be calculated for each tumor lesion, considering the measured tumor-bound activity, the injected activity dose, and the body weight and height of each patient. SUV values will be compared with the degree of CAIX expression determined by immunohistochemistry, using a 5-point scale.

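### The planned SUVmax analyses in section 8.8.2 make no allowance for partial-volume loss in small lesions, which can create an uptake-diameter link and, to a lesser extent, inflate the FDG-89Zr correlation

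*Combined protocol and SAP*

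**What the plan says.** Section 5.2.3 fixes the uptake metric: "SUVmax will be used for tumor tracer-uptake; SUVmean for measuring uptake in healthy organs and blood pool". Section 5.2.3.2 lists what enters the calculation: "SUVs will be calculated for each tumor lesion, considering the measured tumor-bound activity, the injected activity dose, and the body weight and height". Lesion size and a recovery coefficient are not on that list.

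The lesions measured are those read as positive ("Quantification of positive lesions as defined by evaluation reports for" the two tracers), and the 89Zr-TLX250 reading "will be made on the basis of visual examination only". Neither step sets a minimum diameter. The only size requirement is the patient-level one in section 4.2, "with at least one measurable metastatic lesion according to RECIST and/or PERCIST", which leaves a patient's other lesions free to be of any size.

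Section 8.8.2 then plans two analyses of these values. The first is the diameter test: "Link between uptake and lesions location and lesions diameter on CT will be tested". The second is the relation between FDG and 89Zr uptake, given as a rank "coefficient (Spearman test" with no covariate. The documents state no scanner resolution, no reconstruction settings and no expected lesion SUV or diameter.

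**The concern.** A PET scanner blurs the image. When a lesion is not much larger than the spatial resolution, part of its signal spreads into the surroundings and its measured peak falls below the true value. The loss grows as the lesion shrinks, and it affects both tracers in the same lesion.

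This has two consequences. The diameter test is exposed directly, because the artefact is itself a positive uptake-diameter association. It also runs the same way as the background in section 1.2, where "associations with tumor size were significant for CAIX" in the positive direction, so an artefact could pass for confirmation. The FDG-89Zr correlation is exposed indirectly: diameter lowers both SUVs together, and ranking the values does not remove a shared cause.

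At stake is what these two results can be taken to show, in a pilot whose results are meant to inform the case for CAIX as an imaging and therapeutic target.

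**Working it through.** The plan gives no figure to reproduce. Section 8.2 says that the 12 patients have no statistical basis, and no expected correlation is stated. The check is therefore a simulation in which the truth is known to be null.

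**Inputs from the documents:** SUVmax for both tracers; positive lesions only; no size floor; no size correction; plain Spearman.

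**Assumed inputs, not in the documents:**
- resolution (FWHM) 6 mm for FDG and 7 mm for 89Zr
- log-normal diameters with log-SD 0.5 and median 12-20 mm, or 30 mm
- median true SUV 6 for FDG and 2-5 for 89Zr, each with log-SD 0.4-0.6
- background SUV 1.5 for FDG and 1.0 for 89Zr
- a lesion counts as visible when its measured value exceeds 1.5 times background on both tracers

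True FDG uptake, true 89Zr uptake and diameter are mutually independent.

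**Step 1: peak recovery.** For a sphere of radius R blurred by a three-dimensional Gaussian with s = FWHM/2.355:

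RC = erf(R/(√2·s)) − √(2/π)·(R/s)·exp(−R²/(2s²))

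For a 10 mm lesion at 7 mm: s = 7/2.355 = 2.97 and R/s = 5/2.97 = 1.68, so RC = 0.907 − 0.326 = 0.58. At 6 mm resolution the same lesion gives 0.72. At 20 mm diameter and 7 mm resolution RC is 0.99.

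**Step 2: measured SUV** = background + (true − background) × RC. A true 89Zr SUV of 5 reads as 1 + 4 × 0.58 = 3.3 in a 10 mm lesion and 1 + 4 × 0.99 = 5.0 in a 20 mm lesion. Diameter alone produces that difference.

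**Step 3: null correlations in lesions visible on both tracers.** Ranges run over the assumed uptake levels and spreads.

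| Median diameter | 89Zr SUVmax vs diameter | FDG vs 89Zr SUVmax |
|---|---|---|
| 12-20 mm (whole range) | 0.13-0.60 | 0.03-0.32 |
| 15 mm | 0.21-0.47 | 0.06-0.22 |
| 30 mm | below 0.1 | 0.01-0.03 |

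Every true value is 0. As a control, with no partial-volume loss and 60 lesions, the nominal 5% tests reject 4.9% (FDG-89Zr) and 4.8% (89Zr-diameter) of the time.

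**Step 4: dependence on contrast.** The loss scales with lesion minus background. Over all lesions, at median diameter 15 mm and log-SD 0.4, the null FDG-89Zr rho is 0.28, 0.25, 0.20, 0.14 and −0.01 for median 89Zr SUV of 5, 3, 2, 1.5 and 1. At background level there is nothing to lose and the bias vanishes.

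**Step 5: remedies.** In lesions of at least 3 × 7 = 21 mm, both null correlations fall to about 0. A partial Spearman given diameter removes most of the FDG-89Zr bias but can leave up to about 0.10 over all lesions, with about 11% rejection in 60 lesions at median 15 mm.

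**Step 6: lesions retained at 21 mm or more** is 1 − Φ(ln(21/median)/0.5):
- median 12 mm: 1 − Φ(1.12) = 13%
- median 15 mm: 1 − Φ(0.67) = 25%
- median 20 mm: 1 − Φ(0.10) = 46%

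**The case against.** The strongest case on the other side concerns size and consequence.

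- **The FDG-89Zr bias depends on inputs that nobody has stated.** Simulating every lesion, seen or not, at high 89Zr contrast gives a spurious rho up to about 0.52. But the plan quantifies positive lesions, and section 1.3 puts CAIX expression at only 25% of TNBCs, so low contrast may be common. This stands: with the visibility restriction the range falls to 0.03-0.32. The diameter artefact survives the same restriction much better.
- **Adjusting for diameter is not a clean replacement.** It leaves residual bias and, if CAIX truly rises with tumour size, may remove real association. This stands, and is why the adjusted coefficient should be a sensitivity analysis only.
- **The plan attaches no biological reading to either result.** It says only that they will be tested or calculated. This is also correct. The risk lies in how a positive result would be read, and one sentence in 8.8.2 can settle that beforehand.
- **The consequences are limited.** Neither analysis is a listed objective or endpoint of this descriptive 12-patient pilot. That lowers the priority, but the planned diameter test still cannot separate biology from blurring as written.

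A reader might infer that any positive FDG-89Zr correlation here would be pure artefact, or that the primary result is compromised. The documents support neither. The first needs lesion sizes and uptake levels that they do not give. The second fails because the primary endpoint in section 2.1.2 is a set of lesion-count ratios, positivity is judged visually, and SUV does not enter.

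**Conclusion.** The point holds for the diameter test and, more weakly, for the FDG-89Zr correlation. With SUVmax taken in all positive lesions and no size floor or correction, partial-volume loss alone can give a 89Zr-diameter rho of about 0.13-0.60 at median diameters of 12-20 mm. The FDG-89Zr correlation is inflated by about 0.03-0.32 over the same range. If typical lesions are near 30 mm, both effects are small (below 0.1, and 0.01-0.03).

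These figures rest on the assumed resolution, diameters, uptake levels and visibility threshold, and they treat lesions as independent; clustering of lesions within patients is a separate matter. The omission itself and the direction of the bias do not depend on the exact values chosen. The remedy is cheap and worth adopting.

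**What to change.** Keep the planned Spearman correlation and diameter test. Add to section 8.8.2:

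1. A prespecified repeat of both analyses in lesions whose CT diameter is at least 3 times the scanner's measured resolution, using the larger of the two tracers' values. State that resolution in the plan.
2. A partial Spearman correlation of FDG with 89Zr SUVmax given CT diameter, labelled as a sensitivity analysis.
3. A sentence saying that an uptake-diameter link will be read as biology only if it persists in the size-restricted set.

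The cost is SAP wording and a few lines of analysis. CT diameters are already needed for the planned test, so patients undergo nothing extra. There are two downsides. The repeat uses fewer lesions (about 13-46% under the assumptions above at medians of 12-20 mm), so a null result there will be imprecise. The diameter-adjusted coefficient leaves some bias and may remove some true size-related association; the report should say so.
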